2.1.4 Safety Endpoints

Safety evaluations will include adverse event (AE) and serious AE (SAE) reporting, electrocardiograms, vital signs (temperature, respiratory rate, blood pressure, and heart rate),

physical examination, body weight/BMI, knee and linear height, laboratory parameters (hematology, biochemistry, and urinalysis), urine pregnancy tests for FOCBP, radiographic imaging and whole body computed tomography (WBCT), concomitant medication reporting, and the age-appropriate C-SSRS.

Adverse Event Variables

Adverse Event Observation Periods

- A Pre-treatment AE is an AE with an onset date before the first dose of study drug.
- TEAEs are AEs with (first dose date of study drug) \leq (AE start date) \leq (last dose date of study drug +7 days for all AEs, i.e., non-serious and serious AEs).
 - A chronic TEAE is a TEAE with an onset date during chronic treatment
 - A flare-up TEAE is a TEAE with an onset date during flare-up treatment
- Post-treatment AEs are AEs with a start date $>$ last dose date + 7 days for All AEs (non-serious and serious AEs).

Note that subjects may have multiple independent flare-up treatment cycles, each potentially with associated AEs, within the study.

For the efficacy interim analysis and final analysis, treatment emergence for chronic or flare-up treatment is determined based on the subject's dosing diary. For all other pre-lock analyses, treatment emergence is determined using the subject's planned dosing log if insufficient diary data is available, with the date of the extract of data for the interim analysis used as the end date for TEAE assignment purposes.

Any AE with a missing start date is considered TEAE. For TEAEs that have a partial date where the day is missing, if the month is the same month as a flare-up treatment was given, then the TEAE will be defined as a TEAE associated with flare-up dosing.

All AEs (including SAEs) will be coded using a current or recent version of MedDRA. Adverse event severity will be assessed and reported according to criteria defined in the protocol (mild, moderate, severe). Adverse event causality will also be assessed in terms of relationship to study drug and reported according to criteria described in the protocol (not related, possibly related, probably related, definitely related).

The occurrence of AEs (including SAEs) will be recorded from the time of signed informed consent until the end of the study.

Deaths

Deaths after the first dose of study drug are either on-treatment or post-treatment:

- Deaths on-treatment: deaths occurring after the first dose of study drug and up to 7 days after the last dose of study drug
- Death post-treatment: deaths occurring more than 7 days after the last dose of study drug until 30 days after last dose of study drug

Laboratory Safety Variables

Clinical laboratory data will include hematology, biochemistry (including lipids and serum pregnancy test (when applicable)), and urinalysis. Clinical laboratory values will be converted to conventional units; conventional units will be used in all listings and tables.

Hematology, biochemistry, and urinalysis data will be collected at Screening and every 6 months (Months 6, 12, 18, and 24). For subjects receiving flare-up treatment, blood and urine samples will be collected every 12 weeks during safety assessments until the end of the flare-up cycle.

The laboratory parameters will be classified as listed in [Table 5](#).

Table 5. Clinical Laboratory Parameters

Biochemistry:	
Sodium	Globulin
Potassium	Alkaline phosphatase (ALP)
Chloride	Aspartate aminotransferase (AST)
Bicarbonate	Alanine aminotransferase (ALT)
Blood urea nitrogen	Gamma glutamyl transferase (GGT)
Creatinine	Uric acid
Calcium	Total thyroxine (T4)
Inorganic phosphorous	Free T4
Glucose	Thyroid-stimulating hormone
Total bilirubin	Amylase
Total proteins	Lipase
Albumin	
Lipid Profile:	
Triglycerides	High-density lipoprotein (HDL)
Total cholesterol	Low-density lipoprotein (LDL)
	Very low-density lipoprotein (VLDL)
Hematology:	
Hemoglobin	Platelets
Hematocrit	White blood cell count (including differentials)
Red blood cell count	Neutrophils
Packed cell volume	Lymphocytes
Mean corpuscular volume	Monocytes
Mean corpuscular hemoglobin	Eosinophils
Mean corpuscular hemoglobin concentration	Basophils
Urinalysis¹:	
pH	Blood (free hemoglobin)
Protein	Nitrite
Glucose	Urobilinogen
Ketones	Specific gravity
Bilirubin	Color & appearance

¹ If results are abnormal, then a microscopic evaluation will be completed.

Electrocardiogram Variables

A 12-lead electrocardiogram (ECG) will be performed at Screening and every 6 months (Months 6, 12, 18, and 24). Mean heart rate, RR, PR, QRS, QT, QTcF, and QTcB will be determined using centralized readings.

The abnormal ECG categories are defined as follows:

Rhythm

- Atrial premature complexes
- Ventricular premature complexes
- Sinus arrhythmia
- Sinus tachycardia

Conduction

- Nonspecific intraventricular conduction delay
- Right bundle branch block
- Incomplete right bundle branch block
- Left posterior fascicular block
- Left bundle branch block
- Incomplete left bundle branch block

Morphology/Chamber Enlargement

- Left ventricular hypertrophy
- Left ventricular hypertrophy with repolarization abnormality

Axis Deviation

- Right axis deviation
- Left axis deviation

Myocardial Infarction

- Pathologic Q waves
- Acute ST elevation MI
- Acute non-ST elevation MI

ST Segment/T Waves/U Waves

- Early repolarization
- Nonspecific ST and T wave abnormality
- Nonspecific ST elevation
- Nonspecific U wave abnormalities

Vital Signs Variables

Vital sign variables include heart rate, systolic blood pressure, diastolic blood pressure, respiratory rate and temperature. These assessments will be performed at Screening, every 3 months (Months 3, 6, 9, 12, 15, 18, 21 and 24), on Flare-up Cycle Safety Day 1 and then every 12 weeks thereafter until treatment of the last flare-up or traumatic event within a flare-up cycle is completed.

Columbia-Suicide Severity Rating Scale

In accordance with the Guidance for Industry: Suicidal Ideation and Behavior: Prospective Assessment of Occurrence in Clinical Trials, 2012, all subjects ≥ 8 years old who are receiving palovarotene will be assessed for suicidal ideation and behavior using the C-SSRS at Screening and every 3 months (Months 6, 9, 12, 15, 18, 21, and 24); and as part of every Flare-Up Cycle Safety Assessment. The adult form will be used for subjects ≥ 12 years old and the pediatric form will be used for subjects 8 to 11 years old.

Knee and Hand/Wrist Radiographs and WBCTs for Assessment of Bilateral Hand/Wrist and Knee Epiphyseal Growth Plate

All subjects under the age of 18 years enrolled into the MOVE Trial will undergo hand/wrist radiographs (posterior/anterior (PA) view, preferably on the left side) and knee radiographs (AP view) at baseline and every 6 months (Months 6, 12, 18, and 24) to determine bone age (hand/wrist only) and skeletal maturity. Knee and hand/wrist radiograph assessments will be performed at Months 3, 9, 15, 21, etc. in those subjects who (1) received flare up dosing in the period of time since their last assessment; and (2) had not achieved 100% skeletally maturity on their last assessment. Once a subject has achieved 100% skeletal maturity (i.e., epiphyseal closure of all assessed growth plates) as determined by the knee and hand/wrist radiographs, further radiographs will no longer be necessary. Determination of epiphyseal closure requires consensus, with differences in the two assessments undergoing adjudication.

Although the WBCT scans obtained in the NHS and MOVE Trial are used primarily to quantify change in HO volume, they will also be used to assess for potential adverse effects on bilateral hand/wrist and left knee growth plates as well as long bone growth of growing children.

All radiographs and WBCT scans will be assessed by two independent musculoskeletal radiologists at a central imaging laboratory using standardized procedures to ensure consistent and accurate assessment. Bone age will be the average of the two independently assessed bone ages.

The following parameters will be assessed:

- Hand/wrist and knee radiograph images
 - Epiphyseal growth plate abnormalities assessment. Abnormalities to be reported include:
 - Frayed metaphyseal edge
 - Cupping
 - Calcinosis (punctate or streaky calcifications, not orderly closure of the physes)
 - Widening of the epiphyses
 - Sclerosis of the adjacent growing bone (metaphyseal edge)
 - Under-mineralization or osteopenia of the adjacent growing bone
 - Dense metaphyseal lines (also known as growth recovery lines)
 - Epiphyseal growth plate closure assessment
 - Bone age (years, months), if applicable (hand/wrist only)

- Hand/wrist and knee WBCT safety images
 - Epiphyseal growth plate abnormalities assessment

Standardized Stadiometry and Knee Height for Assessments of Linear Growth

Subjects under the age of 18 years enrolled with open epiphyseal growth plates will have linear growth assessments (in triplicate) by stadiometer at Screening and every 6 months (Months 6, 12, 18, and 24). Measurement of knee height using a standard caliper will also be performed (in triplicate) at Screening and every 6 months (Months 6, 12, 18, and 24). Once a subject is 18 years old, triplicate linear growth and knee height measurement will no longer be required.

WBCT Measurements of Femur and Tibia Lengths

Although the WBCT scans obtained in the NHS and MOVE Trial are used primarily to quantify change in HO volume, they will also be used to assess the length of the femur and tibia bilaterally on all subjects aged 17 years and below.

Evaluation of Bilateral Hips by WBCT Safety Read

Although the WBCT scans obtained in the NHS and MOVE Trial are used primarily to quantify change in HO volume, they will also be used to assess potential adverse effects on the femoral head related to avascular necrosis of the hip (AVN).

Two independent radiology reviewers will qualitatively assess the hip joints on WBCT scan to determine whether there is evidence of AVN. Discrepancies in the reads will be adjudicated. Each hip will be assessed for presence or absence of AVN and, if present, the degree of change from the baseline scan and previous scan.

Trauma Leading to Flare-up

In MOVE, subjects can initiate flare-up dosing for substantial high-risk traumatic events likely to lead to a flare up. A listing of traumatic events and whether the trauma resulted in a confirmed flare-up will be generated.

2.1.5 Imaging Performance and Quality Metrics

The imaging Independent Review Charter (V7.1) describes the process for reading efficacy and safety imaging in the MOVE and NHS studies. It also describes an exercise comprised of secondary reviews, i.e., rereads of a subset of cases by the independent reviewers, of low-dose WBCT efficacy, radiograph and low-dose WBCT safety review types. The goal of the exercise is to characterize the intra-reader agreement and the inter-reader agreement for each of these review types.

Intra-Reader Agreement

The imaging vendor will randomly select sixteen study subjects for WBCT efficacy, eight study subjects for WBCT safety and four study subjects for radiograph read types, with a minimum of two timepoints each, for re-evaluation by the same reviewer at least 3 weeks after the initial radiology review. Discrepancies identified within the completed secondary review cases will be reviewed by the vendor as described below:

Discrepancies are defined as below:

- Low-dose WBCT Efficacy Review Any difference in post-TP1 scans as follows:
 - disagreement on the presence/absence of new HO in any region in the post-TP1 scan compared to the TP1 Consensus scan
 - $[(\text{diff change}/(\text{mean}(\text{change})) > 20\% \text{ AND } |\text{diff change}| > 10000)] \text{ OR } |\text{diff change}| > 25000$, where diff change is the difference in the change in new HO compared to the TP1 consensus scan between secondary read and the original read and mean (change) is the average of the change in new HO volume.

- Radiograph Review:

Any difference as follows:

- any difference in the assessment of presence of epiphyseal abnormalities in either the knee and/or hand/wrist (i.e., No vs. Not Evaluable vs. Yes)
 - any difference in the assessment of any epiphyseal abnormality change from TP1 and/or from prior timepoint in either the knee and/or the hand/wrist (i.e., not present vs. no change vs. improved vs. worse vs. unknown)
 - any difference in selected epiphyseal abnormality(ies) per location
 - any difference in epiphyseal growth plate closure assessment (i.e., no (closed) vs. not evaluable vs. yes, partially closed vs. yes, open for any location (distal radius, distal ulna, proximal tibia, or distal femur, as applicable))
 - any difference in skeletal maturity assessment
- Low-dose WBCT Safety Review:

Any difference as follows:

- any difference in the assessment of presence of femoral head abnormalities (i.e., no vs. not evaluable vs. yes)
- any difference in the presence of hand/wrist and/or knee epiphyseal abnormalities (i.e., no vs. not evaluable vs. yes)

- any difference in the assessment of any epiphyseal abnormality change from TP1 and/or from prior timepoint in either the knee and/or hand/wrist (i.e., not present vs. no change vs. improved vs. worse vs. unknown)
- any difference in selected abnormality(ies) per location.

Given the granularity of the discrepancy evaluation, discrepancies of 30% or more are expected to occur for each review type.

Inter-Reader Agreement

To determine inter-reader agreement, the radiologists participating in primary radiology reviews will read a subset of eight study subjects for WBCT efficacy, eight study subjects for WBCT safety and four study subjects for radiograph read types, with a minimum of two timepoints each, randomly selected by Parexel's image management and review system at least 3 weeks after the initial radiology review. Discrepancies identified within the completed secondary review cases will be reviewed by Parexel as described below. Discrepancies are defined in IRC Section 14.1.1 (Intra-Reader Agreement).

If a secondary review results in discrepancies for more than 30% of the timepoints for a reviewer for each review type, Parexel medical personnel will review the discrepancies to assess whether preventative actions as described in IRC Section 14.2 (Quality Monitoring) are required.

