2.4.6 Analyses of Imaging Performance and Quality Metrics

Intra-Reader Agreement

For low-dose WBCT efficacy reviews, secondary reads will be summarized for the count and frequency of discrepancies for the post-baseline timepoints. Coefficients of variation, i.e., ratios of the standard deviation to the mean will also be computed by region and overall, for volumes of HO and for volumes of new HO, i.e., differences between timepoints.

For radiograph review and low-dose WBCT safety review, counts and frequencies for differences will be summarized.

Inter-Reader Agreement

Summary identical to those described above for intra-reader agreement will be performed to describe inter-reader agreement.

Summaries of differences for the primary reads, e.g., adjudication rates, will also be summarized.

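### The reader-discrepancy rule for WBCT efficacy reads omits absolute-value bars on its relative term, so differences of more than 10,000 and up to 25,000 count in one direction only

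*SAP*

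**What the plan says.** SAP 2.1.5 (Intra-Reader Agreement) sets two ways for a WBCT efficacy re-read to be discrepant at a timepoint after TP1.

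- A qualitative one: "disagreement on the presence/absence of new HO in any region in the post-TP1 scan compared to the TP1 Consensus scan".
- A volumetric one. Write D for diff change and M for mean(change). The printed rule is: (D/M > 20% and |D| > 10,000) or |D| > 25,000. For D the text says "diff change is the difference in the change in new HO compared to the TP1 consensus scan between secondary read and the original read"; for M, "mean (change) is the average of the change in new HO volume".

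The bars stand on both volume limits and not on the ratio. No unit is printed; mm³ is inferred from the rest of the SAP.

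For inter-reader agreement, SAP 2.1.5 points to Section 14.1.1 of the imaging charter, which bears the title of the intra-reader section. The inter-reader paragraph also sets the action level: "If a secondary review results in discrepancies for more than 30% of the timepoints for a reviewer", vendor medical staff assess whether preventative action is needed. On reporting, SAP 2.4.6 says "secondary reads will be summarized for the count and frequency of discrepancies for the post-baseline timepoints". It adds coefficients of variation for HO and new HO volume, and adjudication rates for the primary reads.

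**The concern.** An agreement measure should give the same answer whichever read came first. D is a plain difference; if it were already a magnitude, the bars on the two volume limits would be redundant. With positive M, a negative D makes D/M negative, so it can never exceed +20%. In that direction the only volume test left is the 25,000 limit. The opposite disagreement, equal in size, is caught from 10,000 upwards.

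At stake is how reading quality is described for the images behind the primary endpoint. The exercise is small (16 subjects for intra-reader and 8 for inter-reader WBCT efficacy, at least two timepoints each), so a few lost flags can move a reader from above 30% to below it.

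**Working it through.** The SAP gives no figure to reproduce for this rule. It says discrepancies of 30% or more are expected for each review type, but supplies no inputs for that. The check is therefore the logic of the rule, followed by illustrations under stated assumptions.

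**1. Worked pairs.** D = secondary minus original, and M = the average of the two reads' changes.

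| Original | Re-read | D | D/M | As written | With bars on ratio |
|---|---|---|---|---|---|
| 40,000 | 25,000 | −15,000 | −15,000/32,500 = −46% | no | yes |
| 25,000 | 40,000 | +15,000 | +46% | yes | yes |
| 60,000 | 36,000 | −24,000 | −24,000/48,000 = −50% | no | yes |
| 100,000 | 85,000 | −15,000 | −15,000/92,500 = −16% | no | no |
| 60,000 | 30,000 | −30,000 | −67% | yes | yes |

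If D is original minus secondary, the first and third rows become yes as written and the second becomes no. A negative M also reverses the direction.

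**2. Where the bars matter.** The two versions differ only when 10,000 < |D| ≤ 25,000 and |D| > 0.2 × M. A difference of 10,000 needs M below 10,000/0.2 = 50,000; one of 25,000 needs M below 25,000/0.2 = 125,000. From M = 125,000 upwards the two versions agree.

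**3. Flag rates under normal error.** Assume D is normal with mean 0 and standard deviation SD, and M is positive and at most 50,000, so that |D| > 10,000 always exceeds 20%. The SDs are assumptions; the documents give none.

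- With bars: 2[1 − Φ(10,000/SD)].
- As written: [Φ(25,000/SD) − Φ(10,000/SD)] + 2[1 − Φ(25,000/SD)] = [1 − Φ(10,000/SD)] + [1 − Φ(25,000/SD)].

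| SD | 1 − Φ(10,000/SD) | 1 − Φ(25,000/SD) | With bars | As written |
|---|---|---|---|---|
| 7,500 | 0.0912 | 0.0004 | 18.2% | 9.2% |
| 10,000 | 0.1587 | 0.0062 | 31.7% | 16.5% |
| 12,500 | 0.2119 | 0.0228 | 42.4% | 23.5% |
| 15,000 | 0.2525 | 0.0478 | 50.5% | 30.03% |

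At SDs of 10,000 and 12,500 the expected rate exceeds 30% with bars and not as written. At 15,000 both exceed it, the written rule barely.

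**4. Allowing for larger volumes.** I simulated new HO volumes from gamma distributions with the means and SDs of SAP Table 1. Reader error was symmetric, with an assumed coefficient of variation of 10% to 50% plus 0 or 5,000 mm³ of additive error. The written rule missed 24% to 43% of the volume discrepancies that the rule with bars found for single regions, 13% to 28% for the hip alone (Table 1 mean 81.17 thousand mm³), and 18% to 35% for sums of one to three regions. Of re-reads lower by 10,000 to 25,000, the rule with bars itself counted between 25% and 94%.

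**5. The 30% trigger.** Assume 16 independent post-TP1 timepoints for a reviewer. More than 30% of 16 is more than 4.8, so at least 5. With a true discrepancy rate of 40%, the binomial probability of reaching 5 is 0.83 if none are missed, 0.55 if a quarter are missed (rate 0.30) and 0.20 if half are missed (rate 0.20).

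**The case against.** The strongest reply is that this is a copying slip with little consequence. The SAP summarises an imaging charter that is not among the documents; the charter may carry the bars, and the vendor may have applied a two-sided test throughout. The bars on |D| in the same clause suggest that magnitude was meant. That stands as a reason to check the charter first, and it limits the severity. It does not make the printed rule right. Loss of the bars in text extraction cannot be excluded, but bars survive twice in the same expression.

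A reader might infer that every re-read lower by 10,000 to 25,000 goes uncounted. The documents do not support that. The order of subtraction is only implied, so higher re-reads may be the ones lost. A presence/absence disagreement in any region is flagged whatever the sign. Differences at or below 20% of the mean would not count after correction either.

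A reader might also infer that reader error on the primary endpoint is under-reported as a whole. That goes too far. SAP 2.4.6 also reports coefficients of variation and adjudication rates, neither of which uses this ratio. Under SAP 2.4.4 the primary analysis takes adjudicated volumes, or the average of the two readers, so the re-read exercise does not enter it.

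Finally, the trigger only prompts a vendor review, and the SAP already expects discrepancies of 30% or more. No efficacy conclusion depends on it.

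**Conclusion.** The rule is wrong as written, at minor severity. Taken literally it is one-sided for differences of more than 10,000 and up to 25,000 that exceed 20% of the mean. Lower re-reads are missed if D is secondary minus original and M is positive; higher re-reads are missed if the order is reversed. The reported intra-reader discrepancy frequency is then too low. So is the inter-reader frequency, and the 30% trigger is weaker, if charter Section 14.1.1 has the same form.

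The size depends on re-read variability that the documents do not give. For mean changes up to 50,000, and SDs from 7,500 to 12,500, the written rule flags roughly half of what the two-sided rule would. At SD 15,000 it flags about three-fifths (30.03/50.5). The loss shrinks as mean change grows and disappears from 125,000. These figures cover the volume criterion alone; overlap with the presence/absence criterion would reduce the loss.

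**What to change.** In SAP 2.1.5 write the relative term as |diff change| / |mean(change)| > 20%. With bars on both parts, neither the order of subtraction nor a negative mean affects the result. State how a zero mean is handled, and whether the volume rule is applied per region or to the whole body. Confirm that charter Section 14.1.1 reads the same way, and correct whichever document lacks the bars.

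Then check the program that produced the discrepancy counts. If it used the magnitude of the ratio, only the text changes. If it used the signed ratio, recount the intra- and inter-reader discrepancies and compare each reviewer with the 30% level again.

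The cost is one correction to the formula and a small recount, with a possibly higher reported discrepancy rate. SAP 3.3 places the imaging-performance analyses in the interim CSR and does not plan to rerun interim CSR analyses for the final one, so a recount would need a stated exception.

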2.1.6 Pharmacokinetic Endpoints

Pharmacokinetics of palovarotene dosing will be assessed at the first 3-month safety assessment during chronic-based treatment; if samples cannot be obtained during the first 3-month safety assessment, then they can be obtained during any subsequent 3-month safety visit.

Pharmacokinetics will also be assessed twice during flare-up dosing: once during the 20 mg regimen at any time between Study Days 4 to 28, and once during the 10 mg regimen at any time between Study Days 32 and 84, for the first treated flare-up only. If this is not possible for the first treated flare-up, pharmacokinetic blood samples can be obtained during any subsequent flare-up dosing. Pharmacokinetic blood samples will be collected at pre-dose and 3, 6, 10, and 24 hours post-dose.

The following parameters will be determined where possible by model independent analysis using WinNonlin™: $C_{\max,ss}$, $C_{\min,ss}$, $T_{\max,ss}$, AUC_{0-24ss} , λ_z , $t_{1/2z}$, and CL/F.

The determination of palovarotene plasma concentrations will be performed using a validated LC-MS/MS method.

